6.4. Covariates and Subgroups

The protocol does not define any formal subgroup analyses, and the study is not adequately powered to perform subgroup analyses.

6.5. Missing Data

For primary BV recurrence endpoint:

For the mITT analysis population, the BV status of subjects whose status cannot be determined by the TOC visit (visit 4) for any reason will be considered ‘treatment failure’, including subjects who discontinued early from the study and lack of treatment effect.

For the PP analysis population, subjects whose BV status cannot be determined by the TOC visit for any reason will be excluded from the analysis.

For secondary endpoints, missing values will be further excluded from the mITT and PP populations.

6.6. Interim Analyses and Data Monitoring

The study will be monitored to determine if any of the safety halting rules described in section 8.6 in the protocol are met. The DSMB will meet and review safety data and enrollment data at specified times during the course of study and at a study closeout meeting, as defined in the section 8.7.2 in the protocol and the DSMB Charter.

There are no planned interim efficacy analyses for this study.

Further enrollment will be halted for DSMB review/recommendation if any of the following are reported.

1. If one or more participants experience an SAE judged by an investigator to be related to study IP
2. If two or more participants experience an AE that is judged to be Grade 3 and related to study IP
3. An overall pattern of symptomatic, clinical, or laboratory events that the DMID Medical Monitor or DSMB consider associated with study drug and that may appear minor in terms of individual events, but that may collectively represent a serious potential concern for safety

If any of the halting rules are met, the study will not continue with the remaining enrollments or study treatments without a review by and recommendation from the DSMB to proceed. A summary of halting rules is provided in [Table 39](#).

DMID retains the authority to suspend additional enrollment and administration of study product during the entire study, as applicable.

Safety oversight will be conducted by a DSMB that is an independent group of experts that monitors participant safety and advises DMID. The DSMB members will be separate and independent of study personnel participating in this study and should not have scientific, financial or other conflict of interest related to this study. The DSMB will consist of members with appropriate expertise to contribute to the interpretation of the data from this trial.

The DSMB will review study progress and participant clinical and safety data at the following time points:

- An initial organizational meeting will be held prior to the study starting and enrollment of participants.
- At specified times during the course of study as defined in the DSMB Charter.
- Ad hoc meeting convened to address a specific safety concern such as when a halting rule is met or for immediate concerns regarding observations during the study.
- A final closeout review will be held within six months after the database is locked to review all cumulative safety data.

The DSMB will operate under the rules of a DMID-approved charter that will be written at the organizational meeting of the DSMB. Procedures for DSMB reviews/meetings will be defined in the charter. Reports may include enrollment and demographic information, medical history, concomitant medications, physical assessments, clinical laboratory values, dosing compliance, and solicited and unsolicited AE/SAEs. As an outcome of each review/meeting, the DSMB will make a recommendation as to the advisability of proceeding with the study administrations (as applicable), and to continue, modify, or terminate the study.

DMID or the DSMB chair may convene the DSMB on an ad hoc basis according to protocol criteria or if there are immediate concerns regarding observations during the course of the study. The DMID Medical Monitor is empowered to stop enrollment and study treatment if AEs that meet the halting criteria are reported. The DMID Medical Monitor and the ISM (as deemed necessary) will be responsible for reviewing SAEs in real time. The DSMB will review SAEs on a regular basis and ad hoc during the study.

6.7. Multicenter Studies

Safety and efficacy data will be pooled across all clinical sites. Center effects are not anticipated because treatment is self-administered, the sites are using standardized procedures for assessment of unsolicited adverse events, and the study relies on a central laboratory for Gram stain Nugent scoring and BD Max. However, as an exploratory analysis, the primary efficacy outcome measure will be tabulated by clinical site ([Table 13](#)).

6.8. Multiple Comparisons/Multiplicity

There is only one primary endpoint. No adjustments for multiple testing are planned.

7. STUDY SUBJECTS

7.1. Disposition of Subjects

[Table 2](#) will present the number of subjects who failed screening and number of subjects that failed to meet each eligibility criterion. [Table 3](#) will present the disposition of subjects overall and by randomized treatment group. [Table 4](#) summarizes the Safety, mITT and PP analysis population eligibilities by treatment group, and reasons excluded. Subjects will be included in the count for a particular reason for exclusion if they met that criterion. As subjects may meet more than one criterion for exclusion, the “Any Reason” counts may be less than the sum of the individual reason counts. [Listing 1](#) provides the subjects excluded from each of the analysis populations and the reasons for exclusion. A listing of subjects who terminated early from the study or discontinued treatment and the reason for early termination or treatment discontinuation will be included in [Listing 2](#). A listing of subjects who terminated early from the study due to study disruptions from the COVID-19 pandemic will be included in [Listing 3](#).

[Figure 2](#) is a flowchart showing the disposition of study subjects in the safety and efficacy analyses, adapted from the CONSORT statement [7]. It shows the number of subjects eligible, enrolled and randomized, and analyzed for the safety and efficacy analyses, overall and by treatment group.

7.2. Protocol Deviations

[Table 5](#) summarizes subject-specific protocol deviations by deviation category, deviation type, and treatment group for all subjects. All subject-specific protocol deviations and non-subject specific protocol deviations will be included in [Listing 4](#) and [Listing 5](#), respectively.

8. EFFICACY EVALUATION

8.1. Primary Efficacy Analysis

The primary efficacy endpoint for the final analysis is the proportion of subjects with recurrent BV by Test of Cure (TOC, Visit 4 window: Day 85-91) as defined in section 3.3, and in section 6.5 for missing BV status by TOC.

The number of subjects, the proportion of subjects with RBV up to and including V4 will be presented overall and by treatment group with two-sided 95% Wilson confidence interval (no continuity correction). In addition, the difference in proportions between the TOL-463 Vaginal Insert arm and the Placebo group and 95% Newcombe confidence intervals (based on the Wilson CI for the individual proportions) will be presented. See [Table 6](#).

The pseudocode to fit the above analyses is below:

```
proc freq data=dataset;
  Table treatment*cure /chisq riskdiff(Newcombe) binomial(wilson) out=output
  alpha=.05;
run;
```

The primary efficacy analysis will be performed in the mITT population ([Table 6](#)). As a sensitivity analysis, the primary endpoint will additionally be assessed among all subjects in the mITT population except those terminated early due to study disruptions from the COVID-19 pandemic ([Table 7](#)). Analysis of the primary outcome measure will be repeated in the PP analysis population (secondary analysis of primary outcome). See [Table 8](#).

In addition, the rate of recurrence, which considers the amount of observed follow-up time for each participant, will be estimated within each treatment group along with Exact Poisson 95% confidence intervals [8]. We will use a person-time approach as follows. For participants who experience BV recurrence by any visit, the time (in days) of BV recurrence will be defined as the midpoint between the earliest time point of a positive BV diagnosis (post-baseline) and the previous observed time-point. For participants with BV recurrence diagnosed off study, the time (in days) of BV recurrence will be defined as the midpoint between the early termination time point of a positive BV diagnosis off study (post-baseline) and the previous observed time-point. For the participants who did not experience BV recurrence by V4 will contribute the total duration they participated in the study (in days). The participants who withdrew or dropped out early will contribute the number of days they participated in the study. The rate of recurrence = number of recurrence / time each person was observed, totaled for all persons. We will present the estimated recurrence rate in each group and overall, in the mITT population, then repeated in the PP population. See [Table 9](#) and [Table 10](#). The individual time to BV recurrence defined for rate of recurrence is provided in [Listing 7](#).

For efficacy response data, a subject listing of individual Amsel criteria will be provided in [Listing 6](#) for all enrolled subjects, where individual Nugent score will also be included. A summary of Amsel criteria is provided for subjects by visit and treatment group for mITT analysis population in [Table 11](#) and will be repeated in the PP analysis population as a corroborative analysis ([Table 12](#)).

As an exploratory analysis, the primary efficacy outcome measure summaries in the mITT population will be tabulated by clinical site ([Table 13](#)).

As an ancillary analysis, a summary of Nugent score by visit, category (0-3 normal; 4-6 intermediate; and 7-10 BV) and treatment group for subjects in the mITT population will be presented ([Table 14](#)).

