### **5.2.1.2 Handling of Withdrawals**

If a participant withdraws or is withdrawn prior to completion of the study, the reason for this decision must be recorded in the case report forms (CRFs). The investigator will inform the participant that data that has already been collected will be retained and analyzed even if the participant withdraws from this study.

If withdrawal occurs after enrollment, any participant with an ongoing AE will be followed until the AE is resolved or until the participant's condition becomes stable.

Participants who request to withdraw their consent from further study participation after study treatment with IP, will be reminded of the importance of continuing in the study for safety evaluations and will be encouraged to complete the Early Termination Visit if they choose not to complete the remaining study visit(s). The Early Termination Visit procedures are listed in [Section 6.3.4](#). Participants who choose to decline continuation in study participation will no longer be contacted for follow-up.

In the case of participants who fail to appear for a follow-up safety assessment, extensive effort (i.e., three documented contact attempts via phone calls, emails, etc., made on separate occasions) will be made to locate or recall them or at least to determine their health status. Participants who cannot be located after extensive effort will no longer be contacted for follow-up. These efforts will be documented in the participant's records.

If a participant is withdrawn from the study due to an AE that prohibits continued participation in the study, she will be given appropriate care and treatment under medical supervision until the condition has resolved or becomes stable.

Safety and efficacy data will be collected on any participant who is withdrawn from the efficacy endpoint analysis. Withdrawal of participants from the analysis populations is discussed in [Section 10.5.1](#).

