### **6.3.3 Visit 4 (Day 85 [Window: Days 85-91]) Follow-up (TOC)**

- Medical history will be reviewed and updated as appropriate.
- Interim sexual history since the last clinic visit will be collected.
- Vaginal symptoms will be assessed.

---

- A urine pregnancy test will be performed on all participants of childbearing potential.
- Compliance with the study protocol criteria will be assessed; all used and unused study IP packaging will be collected as relevant and recorded.
- Participant memory aid will be collected and reviewed.
- All concomitant medications taken since V3 will be recorded on the appropriate DCF. Previously recorded medications will be updated as appropriate.
- Study personnel will discuss with participants and assess and record all AE/SAEs. Previously recorded AE/SAEs will be updated as appropriate.
- If clinically indicated, a targeted physical examination will be performed by a qualified study clinician.
- A pelvic examination to include examination of external genitalia will be conducted, and swabs and samples taken for analysis of Amsel criteria; KOH and saline microscopy for identification of yeast forms, trichomonas, and clue cells; Gram staining; BD Max test; and for future analysis, for participants who consented to future use of their specimens. Instructions for obtaining vaginal swab specimens for these assessments are outlined in the protocol specific MOP. Gram stain Nugent scoring will be conducted in the Central Laboratory; all other testing will be conducted locally.
- Participants with clinical evidence of VVC based on vulvovaginal signs (edema, erythema, and/or excoriation) and symptoms (vulvovaginal itching, burning, and/or irritation) will have a confirmatory vaginal *Candida* culture and treated.
- Vulvovaginal signs will be assessed and graded by severity, as applicable. A clinical determination for BV recurrence will be made based on evaluation of Amsel criteria. The presence of >2 of 4 Amsel criteria is required for a diagnosis of BV recurrence.
- Participant will complete a satisfaction questionnaire.

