#### **6.3.4 Early Termination Visit**

The V4 assessments and DCFs (see [Section 6.3.3](#)) must be completed at the early termination visit for participants who withdraw, or are withdrawn, or terminated from the study. If a participant withdraws between scheduled visits, the participant will be asked to return to the clinic to perform the V4 assessments.

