8.2. Secondary Efficacy Analyses

Secondary efficacy analyses will be performed in the mITT as the primary population. All the analyses will be repeated in the PP analysis populations as corroborative and sensitivity analyses.

The analysis of Secondary Objective 1, time to BV recurrence will take into account the observed follow-up time for each participant (time-to-event analysis). For this analysis, the outcome will be the time to RBV diagnosis in days from the enrollment visit (day 1). For the participants whose RBV was diagnosed at a scheduled or unscheduled visit, their time of BV recurrence will be defined as the midpoint between the earliest time point of a positive BV diagnosis (post-baseline) and the previous observed time-point. For participants without BV recurrence at or before V4, the BV recurrence endpoint will be coded as censored, with time to recurrence defined as the elapsed time from the first dose of IP, to the earliest of: V4 time-point, the last observed time-point prior to loss to follow-up, or the time-point at which the participant became ineligible for the particular analysis population. Participants with missing time to BV recurrence will be further excluded from analyses in mITT and PP populations, including subjects who had BV recurrence diagnosed off study or subjects who were unknown whether they used any study products. The individual time to BV recurrence defined for secondary objective 1 for mITT and PP populations are also provided in [Listing 7](#).

The null hypothesis for the comparison is that there is no difference in the time to BV recurrence throughout the study between treatment arms, with a two-sided alternative that considers the possibility of a difference in either direction. Kaplan-Meier (KM) curves and associated 95% confidence bands (by treatment groups) will be presented to visually assess the treatment group-specific time-to-recurrence pattern over time. The median time to BV recurrence cannot be calculated because the assumed BV recurrence in the two treatment groups are 20% and 40%. Appropriate quartiles of the time to recurrence will be presented by each treatment group and overall. The KM curves will be presented in [Figure 3](#) for mITT population and in [Figure 4](#) for PP population. The estimate of survival time at which 25% of the subjects have recurrent BV, i.e., 25th percentile of the time to recurrence, by each treatment group and overall will be described in the footnote of the figures.

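### In the mITT recurrence rate, women who leave early without a final BV assessment appear to add days after their BV status was last known, which modestly lowers this descriptive rate

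*SAP*

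**What the plan says.** SAP 8.1 adds a person-time rate to the primary proportion. Its formula reads "The rate of recurrence = number of recurrence / time each person was observed, totaled for all persons", and the rate "will be estimated within each treatment group along with Exact Poisson 95% confidence intervals". No between-arm test of the rate is planned. A recurrence is timed at the midpoint between the positive diagnosis and the previous observed time-point, and off-study diagnoses count as events. For women who leave early the rule is "The participants who withdrew or dropped out early will contribute the number of days they participated in the study". Footnote a of Listing 7 repeats it as Definition 1.

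For time to recurrence, SAP 8.2 censors women without recurrence at the earliest of several points, one of which is "the last observed time-point prior to loss to follow-up".

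Two sections of the Protocol decide whether the end of participation and the last assessment fall on the same day. Section 6.3.4 says the V4 assessments "must be completed at the early termination visit for participants who withdraw, or are withdrawn, or terminated from the study", and at V4 (section 6.3.3) "A clinical determination for BV recurrence will be made based on evaluation of Amsel criteria". Section 5.2.1.2, however, only encourages women who withdraw consent to attend that visit. It adds: "Participants who cannot be located after extensive effort will no longer be contacted for follow-up".

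**The concern.** A rate is interpretable when each day in the denominator is a day on which an event could have entered the numerator. A woman who was negative at V2, missed V3 and was closed as lost some weeks later has unknown BV status for those weeks. If they count as days participated, they enter as recurrence-free time.

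SAP Listings 2 and 3 record the study day of early termination and the last completed visit in separate columns, so the plan expects the two to differ. The first column is the natural source for days participated. Footnote a to SAP Table 3 also expects some early terminations before V2 at which the product-dispensing assessment could not be done, and the SAP provides for COVID-19 shelter-in-place terminations. SAP 8.2 drops women with unknown product use from the Kaplan-Meier analysis, but 8.1 has no such exclusion. A woman in the mITT population with no post-baseline assessment could therefore add nothing but unassessed days to Table 9.

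At stake are the level of the rate in each arm and, if dropout or close-out time is unbalanced, the comparison that a reader will draw from the two rates.

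**Working it through.** **Design figures.** The documents give no expected person-time rate. Their design inputs are 40% recurrence on placebo, 20% on TOL-463 and 200 evaluable women (SAP section 5). With 100 per arm at two-sided 5%, power is 87.6%, which agrees with the stated minimum of 85%. Enrolment is 200 / 0.8 = 250, as stated.

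**Inputs from the documents.** Recurrence by the end of 12 weeks (84 days) is P = 0.40 or 0.20. Assessments fall 28, 56 and 84 days after Day 1. Recurrences are timed by the midpoint rule.

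**Assumptions.** The hazard is constant. A fraction d drops out non-informatively, with the last assessment at 0, 28 or 56 days in equal shares. A dropout who is recurrence-free at that assessment adds e further unassessed days. No off-study diagnoses are modelled. The documents give neither d nor e. The 20% planned as non-evaluable is a guide only and is not a dropout rate.

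**Step 1: hazard and recurrence-free share.** h = -ln(1 - P) / 84 gives 6.08 (placebo) and 2.66 (TOL-463) per 1000 days. S(t) = exp(-ht) at 28, 56 and 84 days is 0.8434, 0.7114, 0.6000 (placebo) and 0.9283, 0.8618, 0.8000 (TOL-463).

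**Step 2: a woman followed to V4.** Events are 1 - S(84). Person-days are the interval event probabilities times 14, 42 and 70, plus 84 x S(84).
- Placebo: 0.40 events and 65.93 days.
- TOL-463: 0.20 events and 75.32 days.

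**Step 3: a dropout, averaged over the three possible last assessments.**
- Placebo: 0.1484 events, 24.46 days to the last assessment, 0.8516 recurrence-free at that point.
- TOL-463: 0.0700 events, 26.35 days, 0.9300 recurrence-free.

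**Step 4: rate at d = 0.20.**
- Placebo: (0.8 x 0.40 + 0.2 x 0.1484) / (0.8 x 65.93 + 0.2 x 24.46 + 0.2 x 0.8516 x e) = 0.3497 / (57.64 + 0.1703e).
- TOL-463: (0.8 x 0.20 + 0.2 x 0.0700) / (0.8 x 75.32 + 0.2 x 26.35 + 0.2 x 0.9300 x e) = 0.1740 / (65.53 + 0.1860e).

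| e (days) | Placebo per 1000 days | Change | TOL-463 per 1000 days | Change |
|---|---|---|---|---|
| 0 | 6.07 | - | 2.66 | - |
| 7 | 5.94 | -2.0% | 2.60 | -1.9% |
| 14 | 5.83 | -4.0% | 2.55 | -3.8% |
| 28 | 5.60 | -7.6% | 2.46 | -7.4% |

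With e = 0 the rates recover the underlying 6.08 and 2.66 almost exactly, so stopping at the last assessment removes nearly all the bias. The e = 0 row also describes dropouts who attend the early termination visit.

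**Step 5: other dropout rates.** At e = 14 the fall is about 2% with 10% dropout and about 6% with 30%. At e = 28 it is about 4% and 11% to 12%.

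**Step 6: rate ratio, TOL-463 to placebo.**

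| Dropout TOL-463 / placebo | e = 0 | e = 14 | e = 28 |
|---|---|---|---|
| 20% / 20% | 0.438 | 0.438 | 0.439 |
| 30% / 10% | 0.438 | 0.419 | 0.403 |
| 10% / 30% | 0.438 | 0.458 | 0.479 |

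**Step 7: what enters the numerator.** The downward direction requires that only known recurrences are counted. If the mITT rule that missing status is a treatment failure were carried into the rate, then at d = 0.20 and e = 14 it would be (0.8 x 0.40 + 0.2) / 60.02 = 8.66 per 1000 days on placebo and (0.8 x 0.20 + 0.2) / 68.13 = 5.28 on TOL-463. Both are well above the true values.

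**The case against.** The strongest reply is that SAP 8.1 never says the clock runs to the termination date. Days participated is undefined, and the paragraph opens and closes by speaking of observed time. A programmer could stop at the last observation and be faithful to the text. This stands as a caution: the point rests on the natural reading, not on express wording. It does not dispose of the matter, because the separate columns in Listings 2 and 3 favour the termination day, and two programmers could produce different Table 9 values.

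A reader might also infer that recurrence can be found only by an Amsel examination, so that all later time is unobservable. The SAP does not support that. Sections 4.5.1 and 8.1 count diagnoses made off study, so a later contact can establish status. This affects the remedy as well. If person-time stopped at the last Amsel assessment while later off-study recurrences stayed in the numerator, the rate would be pushed up.

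A third reply is that 8.1 and 8.2 are separately labelled definitions that already treat off-study recurrences differently, so a difference between them is not in itself a contradiction. That is fair. The sharper mismatch is between the dropout rule and the formula in the same paragraph.

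**Conclusion.** The point holds for one group: women in the mITT population who leave early without recurrence and without a final BV assessment. For them the rule, read naturally, counts days on which status was unknown, and the rate is lowered by about 2% to 8% per arm. That range assumes 20% dropout, 7 to 28 unassessed days for every dropout, a constant hazard, non-informative dropout and a numerator of known recurrences. More dropout or slower close-out would enlarge it. Early termination visits or off-study ascertainment would shrink it.

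A reader might conclude that every dropout biases the rate, or that the treatment comparison is distorted. The documents do not support either. Attendees at the early termination visit have an Amsel assessment on their last day and cause no bias. The rate ratio barely moves when dropout and close-out time are balanced. The per-protocol rate (Table 10) is essentially protected, because that population requires an in-window V4 or follow-up to recurrence (SAP 6.3). The primary proportion and the Kaplan-Meier analysis do not use this person-time. This is a small, easily corrected definition in a supportive analysis.

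**What to change.** In SAP 8.1 and in footnote a of Listing 7:

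1. End person-time for participants without recurrence at the last time-point at which BV status was ascertained. That is the last Amsel assessment, including one at the early termination visit, or a later contact at which off-study BV status was established. This keeps the denominator in step with both routes into the numerator.
2. State that the numerator counts only observed or off-study diagnosed recurrences, not treatment failures imputed for missing status.

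The cost is one derived variable, two sentences and slightly less person-time. In the 20% dropout, 14-day case, placebo person-days per woman go from 60.02 to 57.64, about 4% fewer. The days lost carry no information on recurrence.
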